6.3 Adverse Reactions and Precautions

The subjects will be educated as to what to expect during the procedure and the importance of immediately communicating any problems, unusual symptoms, or discomfort, to the investigator during the treatment and throughout the follow-up period. Subjects will also be educated as to what sensations or perceptions could indicate that neurological damage may be starting to occur. They will be told to use their handheld stop sonication button if they perceive anything unusual may be happening so that they can be neurologically assessed. All adverse reactions occurring in this study will be recorded in the Case Report Forms. Each AE will be assessed for its cause (i.e., categorized as definitely, probably, possibly, or unrelated to the device, procedure or disease progression). Alternative treatments resulting from post-surgical changes in neurological status will be captured and reported.

6.4 Criteria for Removal from the Study

The investigator may withdraw subjects from the study as is deemed necessary or deemed to be in the best interests of the subject, such as,

- continued noncompliance with the protocol or study visits,
- severe illness or disability during the study for non-study issues,
- pursuit of subsequent alternative treatment for the same condition, or
- development of intolerable side effects where continued follow-up becomes too burdensome.

In addition, a subject may also chose to exit the study at any time, but will be strongly encouraged to participate in the follow-up visits for safety reasons (continued monitoring of subject safety).

6.5 Rules for Stopping the Study

This study may be stopped, if, in the opinion of the DSMB, serious risks to the health and welfare of subjects are observed that are directly related to the use of the device. The following scenarios would invoke this section of the protocol to stop the study while the cause of the safety concerns is being investigated and to determine relation of these safety events to the device, along with any possible mitigating steps to protect patients from device harm. Either of the following scenarios would create cause for stopping the study to evaluate patient safety:

- Any death that is deemed to be caused by the ExAblate treatment
- 2 or more events of intracranial hemorrhage deemed to be caused by the ExAblate device
- Any other serious, related Unanticipated event that causes significant disability/harm to the subject that is deemed to be the result of the ExAblate device.

Investigator(s) shall promptly report the occurrence of any such events to the Sponsor (i.e. InSightec) and the Sponsor shall promptly initiate review by the DSMB as well as reporting such event(s) to the FDA. Once the DSMB has had an initial assessment of an event of this type, it may recommend stopping the study in order to investigate fully the events and circumstances. This will be communicated to FDA and all IRBs and sites. With full cooperation of the treating investigator and the Sponsor, the DSMB will evaluate the circumstances of the event, determine relation of these events to the ExAblate, and whether any modifications to the protocol or the device must be made to improve safety. The Sponsor will keep FDA informed of the results of the DSMB evaluation and of any potential actions taken by the Sponsor. Once the review is completed and any mitigations are in place, and the DSMB recommends re-opening the study with concurrence by the FDA, then InSightec will communicate this with all sites and their IRBs to begin to re-open and continue the study.

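### Protocol section 6.5 says its three safety triggers stop the study during the investigation, but its procedure holds no treatment until the DSMB, with no deadline, recommends a stop

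*Protocol*

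**What the plan says.** Section 6.5 of the protocol (Rules for Stopping the Study) opens with a discretionary rule: "This study may be stopped, if, in the opinion of the DSMB, serious risks to the health and welfare of subjects are observed". The next sentence reads more firmly: "The following scenarios would invoke this section of the protocol to stop the study while the cause of the safety concerns is being investigated". The same sentence adds that the relation to the device is to be determined in that time. A third sentence says that any of the scenarios "would create cause for stopping the study to evaluate patient safety".

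The three scenarios follow. The first is "Any death that is deemed to be caused by the ExAblate treatment". The second is two or more intracranial hemorrhages attributed to the device. The third is any other serious, related, unanticipated event that causes significant disability or harm and is attributed to the device.

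Then comes the procedure. Investigators report such events promptly, and "the Sponsor shall promptly initiate review by the DSMB" and informs the FDA. After an initial assessment the DSMB has a choice: "it may recommend stopping the study in order to investigate fully the events and circumstances". In the fuller review, "the DSMB will evaluate the circumstances of the event, determine relation of these events to the ExAblate". The study resumes once mitigations are in place and "the DSMB recommends re-opening the study with concurrence by the FDA".

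Section 6.6 gives the site two working days to report a serious adverse event to the sponsor. Section 6.7 contains a separate mandatory stop for events that meet all five of its listed conditions.

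**The concern.** The lead-in to the triggers promises a stop that covers the investigation. The steps that a site and the sponsor would actually follow contain no instruction to pause randomization or treatment, name nobody to order a pause, and set no time by which the DSMB must make its initial assessment. The interval between a trigger being reported and a DSMB recommendation is therefore unregulated.

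The intervention is an ablative lesion in the thalamus. Section 6.1.7 names serious neurological deficit and death as possible, and section 6.2 says that the probability of an adverse effect in brain treatments is unknown. Up to 8 sites treat in parallel (section 5.4), and sham subjects may cross over to active treatment from month 3 (section 4.1.3). If a death or a second hemorrhage had a cause common to the device, the next patient at another site would be exposed to it before anyone was required to pause.

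**Working it through.** This is a comparison of text. The plan has no figure to reproduce.

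**Step 1: what happens after a trigger, in the order of section 6.5.**

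| Stage | Who acts | Time limit | Treatment held? |
|---|---|---|---|
| Event reported to sponsor | Investigator | Prompt (6.5); two working days for an SAE or UADE (6.6) | Not stated |
| DSMB review started, FDA informed | Sponsor | Prompt | Not stated |
| Initial assessment | DSMB | None | Not stated |
| Recommendation to stop | DSMB, optional | None | Only if the DSMB so recommends |
| Full evaluation, including relation to device | DSMB | None | Yes, if a stop was recommended |
| Re-opening | DSMB with FDA concurrence | None | Hold ends |

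The first hold appears in the fourth row and is optional. The lead-in sentence, read alone, would place it in the first.

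**Step 2: does another section impose the hold?**

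- Section 6.7 requires a stop only when all five conditions are met. Two of them are that the event was unexpected and that continuing carries an unreasonable risk. Section 6.2 lists subdural bleeding, bleeding in the treated area, arterial bleeding and death among significant anticipated side effects. A death or hemorrhage can therefore satisfy a 6.5 trigger and still fail the unexpected condition. The third 6.5 trigger is unanticipated by definition, so 6.7 partly covers it, but only with the added finding of unreasonable risk. The 6.7 questions are also posed for Test Arm events, which leaves crossover treatments unclear.
- The protocol's section on the DSMB within 4.1 (numbered 4.1.5) gives the board an advisory role on continuation.
- The SAP plans no interim analysis (section 9), and its safety analyses are descriptive with no stopping rule (section 10.5).

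None of these closes the interval.

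**Step 3: who makes the first attribution?** Section 6.5 does not say. Sections 2.1.1, 6.6 and 6.7 have the investigator classify or consider relatedness, and 6.5 and 6.7 have the DSMB determine it afterwards. The order can be worked out, but 6.5 should state it, because the trigger depends on it.

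**Step 4: an illustration only.** The documents give neither the accrual rate nor the DSMB's response time. Assume that treatments are spread evenly over 52 to 104 weeks and that the interval lasts 1 to 4 weeks. At 3:1, 72 randomized gives 54 ExAblate and 18 sham, and 80 gives 60 and 20. Active treatments then run from 54 (72 randomized, no crossover) to 80 (80 randomized, all 20 sham subjects cross over).

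- Treatments in the interval = treatments ÷ weeks of treatment period × weeks of interval
- Low: 54 ÷ 104 × 1 = 0.52
- High: 80 ÷ 52 × 4 = 6.15

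The range comes mostly from the two assumed durations and applies only if a trigger occurs. The conclusion does not rest on it.

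**The case against.** The strongest reply is that section 6.5 describes one coherent, DSMB-gated sequence. What the scenarios invoke is the section itself, whose first sentence is discretionary. Creating cause for a stop means supplying grounds, not halting automatically. The stop would then follow the initial assessment and cover the full investigation, which fits the lead-in. Most of the wording does lean this way, and a DSMB-gated stop is a legitimate design.

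This reply has force against two stronger readings. A reader might infer that 6.5 flatly contradicts itself. The documents do not compel that, because the sequential reading is available. A reader might also infer that the triggers are circular, since nobody is named to attribute the event and the DSMB decides relation only later. Investigators already make a first relatedness call under other sections, so a provisional call followed by adjudication is workable.

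The gap survives the reply. Even on the sequential reading, nothing says whether treatment continues between the report and the DSMB's initial assessment, and no deadline limits that interval. The duty to act promptly falls on the reporting investigator and on the sponsor in starting the review, not on the DSMB in finishing its assessment.

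**Conclusion.** The point holds as a gap in an operational safety rule, and it should be fixed. It concerns all three triggers and up to 8 sites. The interval has one fixed limit, two working days from site to sponsor, and none after that. Section 6.7 cannot be relied on for deaths or hemorrhages, because both are listed as anticipated. Sample size, power and alpha are unaffected.

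A reader might take the illustrative 0.5 to 6 treatments as an estimate of patients put at risk. The documents do not support that: both durations are assumed, and the plan gives no probability that a trigger occurs. Nor do the documents show that any site treated through such an interval. A reader might also conclude that the triggers should fire on events rated only possibly related. Nothing in the plan requires that. It would change the stopping rule itself and would clash with the causal wording of the bullets.

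The verdict assumes that sites would follow the written steps of 6.5 and that no manual outside these documents already orders a pause.

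**What to change.** Keep the three bullets and their present causal threshold, and make these changes.

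1. In 6.5, state that the investigator or the sponsor makes the first judgment that an event meets a trigger, and that the DSMB adjudicates afterwards.
2. Add to 6.5: *When any listed trigger is reported, the sponsor immediately notifies all sites. Randomization and all treatment procedures (ExAblate, sham and crossover) are suspended until the DSMB completes its initial assessment, within [number] days, and recommends either continuing or a full stop. After a full stop, re-opening follows the existing DSMB and FDA path. Follow-up visits continue throughout.* The sponsor and the DSMB should fill in the number of days. This replaces the sentence that makes a stop optional after the initial assessment.
3. Limit the discretionary opening sentence of 6.5 to safety concerns other than the listed triggers.
4. In 6.7, state that its five-condition stop is additional to 6.5 and does not limit it.

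The cost is a protocol text amendment and, if a trigger is reported, a short pause in elective treatments at every site, including for events that the DSMB later finds unrelated. The stated deadline limits the pause.

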6.6 Adverse Event Reporting

It is the responsibility of the investigator to document all AE's occurring during the course of the study. At each visit, the investigator will evaluate AE's. AE's not previously documented in the study will be recorded on the Adverse Event Log within the CRF. The nature of each event, date and time (when appropriate) of onset, outcome, frequency, maximum intensity, action taken, expectedness, and causal relationship will be recorded. AEs already documented in the CRF (i.e., at a previous assessment) and designated as 'ongoing', should be reviewed at subsequent visits as necessary. If these have resolved, the documentation in the CRF should be completed including an end date for the event.

Standard Code of Federal Regulation (CFR) definitions for Serious Adverse Events (SAEs) will be used for evaluation of adverse events.

SAE [§803.3(aa)(1)] is an injury or illness that:

- *causes death*

- *is life threatening, even if temporary in nature;*
- *results in permanent impairment of a body function or permanent damage to a body structure; or*
- *necessitates medical or surgical intervention to preclude permanent impairment of a body function or permanent damage to a body structure.*

All AEs (related or unrelated) meeting the criteria for an SAE require notification of the sponsor and the reviewing IRB as soon as possible, with subsequent completion of additional paperwork provided by the sponsor fully documenting the course of the event, all treatments, and final outcome. Initial reporting of an SAE should be made to the sponsor no later than two (2) working days after the PI learns of the incident. AE's that do not affect the safety or overall well being of the subject, are mild/moderate in nature, are estimated to be temporary in duration even though the exact end date may not be determined *a priori* (e.g., eye twitch increased from baseline) may be presented and discussed with DSMB to determine their final classification status as a serious or non-serious adverse event.

Standard Code of Federal Regulation (CFR) definitions for Unanticipated Adverse Device Effects (UADEs) will be used for evaluation of this type of adverse event.

UADE [§812.3(s)] means any serious adverse event on health or safety or any life-threatening problem or death caused by, or associated with, a device, if that effect, problem, or death was not previously identified in nature, severity, or degree of incidence in the investigational plan or application (including a supplementary plan or application), or any other unanticipated serious problem associated with a device that relates to the rights, safety, or welfare of subjects.

Any UADEs will be reported to the Sponsor and to the reviewing IRB as soon as possible. However, in no event must this report be made later than two (2) working days after the PI learns of the incident.

6.7 Data Safety Monitoring Board

A Data Safety Monitoring Board will be used to review all AE's on the study. Their role is to evaluate all AE's that occur throughout the study and determine if they are in fact related to the ExAblate, or some other cause. Investigators will monitor all treatments for any AE's, and consider the following questions for AEs in the Test Arm:

- *Was the adverse event serious?*
- *Was the adverse event life-threatening, caused a disability, required or prolonged hospitalization, or caused death?*
- *Was the adverse event device related?*
- *Was the adverse event unexpected?*
- *Is there an unreasonable risk in continuing the trial?*

Adverse Events meeting all the above conditions would require reporting to the FDA, stopping the study pending the results of further investigation, and FDA approval to re-start the study. Following the DSMB review of the event, and if in the opinion of the DSMB, a modification of the study protocol were necessary to provide adequate protection to future study participants, the modification would be implemented prior to reinitiating the investigation. Any such amendment would be reported to the IRB and FDA for their respective approvals to re-start the study as it is required by the applicable regulations.

All adverse events will be assessed for their relationship to the study device or procedure. Standard Code of Federal Regulation (CFR) definitions for SAEs and UADEs will be used in assessment of adverse events.

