ALL imaging exams of this study must be forwarded to the Sponsor in a timely fashion immediately following their acquisition and properly anonymized from all subject identifiers.

4.2.2 Post-Treatment Follow-up – All procedures for follow-up are common between treatment groups..

4.2.2.1 Day 1 Follow-up Procedures:

The neurosurgeon will perform the following exams and make a decision as to whether or not to discharge the subject. Subjects who are found to be neurologically unstable will remain in the hospital until the neurosurgeon determines it is medically indicated to discharge.

- a) Review of medications
- b) physical exam
- c) neurological status

Any adverse events will be recorded and followed. The physician should treat the subject according to their best clinical judgment if adverse events are noted.

4.2.2.2 Week 1

The following evaluations should be performed at Week 1:

- Review of medications
- Physical exam

- Neurological status
- Adverse events
- Blinding form asking if they believe they received the actual treatment or the placebo treatment.

4.2.2.3 Month 1 and 3

The following evaluations should be performed at 1 & 3 months:

- Review of medications
- Physical exam
- Neurological Status
- CRST by blinded site assessor with taping for Central Lab assessment
- QUEST and PHQ-9-depression questionnaires should be completed by the subject
 - NOTE:

At any follow up visit, any subject who scores ≥ 20 on the PHQ-9 questionnaire, the subject should be referred out for psychiatric evaluation. The Columbia Suicide Severity Rating Scale, or like, may be used. Should there be a psychiatric treatment, then this psychiatric treatment should be recorded as an adverse event. A Copy of the psychiatric evaluation should become part of the CRF information as part of the adverse event outcomes and description. The investigator will evaluate whether the subject may continue participation in the study, or should be exited from the study for treatment

- Adverse events
- Blinding form asking if they believe they received the actual treatment or the placebo treatment.
- At Month 3,
 1. All subjects may be un-blinded after completing all Month 3 subject assessment measures.

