6.1 Safety Endpoints

The safety endpoints are:

- Adverse Events (AE's)
- Serious Adverse Events (SAE's)

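### A prolonged hospital stay or a disability that resolves is named in protocol 6.7 but absent from the SAE list in 6.6, and no table in SAP 10.5 would show it

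*Protocol*

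**What the plan says.** **Protocol 6.6** gives four SAE criteria: death; "is life threatening, even if temporary in nature"; "results in permanent impairment of a body function or permanent damage to a body structure"; and "necessitates medical or surgical intervention to preclude permanent impairment of a body function or permanent damage to a body structure". It presents them as the cited regulatory definition. An SAE must first be reported to the sponsor within two working days.

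**Protocol 6.7** puts five questions for events in the Test Arm. The first is whether the event was serious. The second is "Was the adverse event life-threatening, caused a disability, required or prolonged hospitalization, or caused death". The others concern device-relatedness, unexpectedness and unreasonable risk in continuing. The questions combine by AND: "Adverse Events meeting all the above conditions would require reporting to the FDA", together with a halt to the study pending investigation. The same section says the regulatory SAE definitions are used to assess events.

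**Protocol 4.2.1.3 and 4.2.2.1** plan hospital observation until the morning after treatment and foresee longer stays: "Subjects who are found to be neurologically unstable will remain in the hospital" until the neurosurgeon decides on discharge.

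**SAP 6.1** names two safety endpoints, adverse events and "Serious Adverse Events (SAE's"), and has no SAE definition of its own. **SAP 10.5** tabulates all adverse events by body system, preferred term, onset and resolution window, severity and relation to treatment. It lists all SAEs, and repeats the tables for SAEs alone if there are more than 12.

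**The long-term follow-up protocol** repeats the SAE definition in 15.1 and the five questions in 15.2 and 17.2.

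**The concern.** Two outcomes that 6.7 singles out, hospitalization and a disability not limited to a permanent one, are missing from the list that decides whether an event is an SAE. The protocol foresees both. It provides for unstable subjects to stay in hospital, and in 6.1.7 it describes transient neurological deficits from inflammation around the lesion, which it expects to resolve in two to three weeks.

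What is at stake is how visible these events are in the safety report. SAEs are one of the two safety endpoints and the only events with a dedicated listing in SAP 10.5. A subject kept in hospital for several days with a deficit that later clears would appear in the general adverse event tables with a severity grade and a resolution window, and nothing there would show the longer stay. Severity does not stand in for it. The one serious related event reported for the pivotal cohort, in section 18 of the long-term follow-up protocol, was graded moderate.

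**Working it through.** There is no figure in the plan to reproduce. The check sets the two lists side by side and applies the AND rule of 6.7 to each outcome taken alone, assuming that the questions on relatedness, unexpectedness and unreasonable risk are all answered yes.

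| Outcome taken alone | SAE under 6.6 | Meets question 2 of 6.7 | Passes both |
|---|---|---|---|
| Death | yes | yes | yes |
| Life-threatening | yes | yes | yes |
| Permanent impairment (taken as a disability) | yes | yes | yes |
| Intervention to prevent permanent impairment or damage | yes | no | no |
| Disability that resolves | no | yes | no |
| Hospitalization or prolonged stay | no | yes | no |

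The last two rows are the gap. These outcomes satisfy question 2 but fail question 1, because seriousness in 6.7 is judged by the definition used in 6.6.

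Four other provisions might close the gap:

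- **Protocol 6.5.** Treatment-caused death and two or more device-caused intracranial hemorrhages are stopping conditions with no separate seriousness test. The third, general condition requires a serious event.
- **Unanticipated adverse device effects (6.6).** The definition is built on serious events, threats to life, death and unanticipated serious problems.
- **Reclassification by the monitoring board (6.6).** This covers mild or moderate temporary events that do not affect the subject's safety or well-being. It does not clearly reach an event that keeps someone in hospital.
- **Event recording (6.6).** Outcome, maximum intensity and action taken are recorded. Hospitalization is not a named item, though the action-taken field might capture it.

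None of these clearly gives the event SAE status.

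**Size of one event.** The documents give no rate for prolonged stays or resolving disability, so only the weight of a single affected subject can be shown.

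- With 56 ExAblate subjects (the ITT number in section 18 of the long-term follow-up protocol): 1/56 = 0.0179, about 1.8 percentage points.
- With the planned size of 72 to 80 randomized 3:1, the ExAblate arm is 72 × 3/4 = 54 to 80 × 3/4 = 60: 1/54 = 1.9 and 1/60 = 1.7 percentage points.

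The denominator is an assumption. Section 18 labels 56 as ITT, whereas SAP 10.5 uses the Safety population.

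**The case against.** The strongest reply is that little is lost. All adverse events are an endpoint, all are tabulated, SAP section 11 promises listings of all available data, and the monitoring board reviews every event. The list in 6.6 is presented as the device regulation's own definition, so widening it is a preference. The safety analysis is described as descriptive and narrative, so no success criterion changes. Some prolonged stays would be SAEs anyway, because 6.1.7 foresees drug treatment or craniotomy for deficits and such treatment may meet the fourth criterion. The wording of question 2 also does some work: an SAE under that fourth criterion that is neither fatal nor life-threatening can pass question 2 only through hospitalization or disability.

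All of that stands. It narrows the point to classification and display, but it does not supply a table or listing that identifies these outcomes.

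A reader might go further in four ways that the documents do not support:

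- **That the SAP reports only SAEs.** SAP 6.1 and 10.5 cover all adverse events.
- **That question 2 is the protocol's real standard of seriousness, so that the reported SAE rate is too low.** Question 2 is a further filter in a five-part test; seriousness is question 1. Nothing shows that any such event occurred. Multiplying the reported rate would mean inventing a number of extra events. It would also mean tying the one serious related event to a denominator that section 18 does not give for it, although the SAP endpoint covers all SAEs and not only related ones.
- **That the gap in 6.6 is what keeps a neurological deficit with a prolonged stay from triggering 6.7.** Section 6.2 lists neurological deficits among the anticipated side effects, so that event would probably fail the unexpectedness question in any case.
- **That 6.6 misquotes its regulation.** The defect is the mismatch between 6.6 and 6.7.

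**Conclusion.** The point holds as an inconsistency between 6.6 and 6.7 that carries through to the safety report. An event whose only serious feature is a stay beyond the planned night, or a disability that resolves, remains an ordinary adverse event: it receives no SAE classification, two-day SAE notification or SAE listing. It also does not count towards the threshold of 12 for separate SAE tables. If such events occur, the SAE count will not show them, and no other table in SAP 10.5 identifies them.

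The number affected cannot be estimated. Each affected subject is worth about 1.8 percentage points on a denominator of 56, or 1.7 to 1.9 over the planned arm sizes. The conclusion assumes that the event meets no other 6.6 criterion and that seriousness in 6.7 has its 6.6 meaning, as the text of 6.7 indicates. No efficacy result or formal safety criterion depends on it.

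**What to change.** Keep the regulatory SAE definition as cited. In SAP 10.5, add one listing and one count by arm of all events that meet either a 6.6 criterion or question 2 of 6.7. Show which criterion applied, and give numbers of events and of subjects. Include Sham explicitly, because 6.7 poses its questions for the Test Arm only. Repeat the display for the Crossover and combined populations that 10.5 already covers.

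To support this, add two CRF items to the adverse event form: hospitalization beyond the planned overnight stay, and disability. The second needs a short working definition, since 6.7 gives none.

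Separately, 6.6 and 6.7 must be reconciled on whether these outcomes count as serious, as must 15.1, 15.2 and 17.2 of the long-term follow-up protocol. That decision belongs to the sponsor: changing the list in 6.6 would also change what reaches the stopping provisions in 6.5 and 6.7. The SAP display can be added without waiting for it.

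The cost is one extra listing and count, two CRF items, and possibly a less favourable safety summary.
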